## **9.5 Pain medication endpoints based on daily entries in eDiary**

### **9.5.1 Subject mean weekly dose of opioid analgesics from baseline up to Month 6**

Opioids are selected using a list of WHO Drug Dictionary codes maintained in a separate file which will be finalized and stored in the eTMF before breaking the randomization blind.

First, the dose of all opioids will be transformed to the same unit (mg), using [Table 7](#), as needed. Doses will then be converted to equianalgesic doses of oral morphine. The above-mentioned file which includes the list of opioids also includes the corresponding conversion factors.

**Table 7 Conversion of units to mg**

Original unit	Converted unit
FINGERTIP UNIT	400 mg
tsp (teaspoon)	5 mL
tbsp (tablespoon)	15 mL
DROP	0.05 mL

mL is converted to mg by multiplying the volume by the concentration.

For each day on which a subject reported at least one opioid in the eDiary, the total daily dose of opioid analgesics will be derived as the sum of all converted doses for the respective day. For days on which a subject did not report any opioids, the total daily dose of opioid analgesics will be imputed as 0 mg (i.e., no opioids taken on that day) if the subject did record at least one *non-opioid* pain medication in the eDiary on the respective day.

If a subject did not report any pain medications in the eDiary on the respective day, the total daily dose of opioid analgesics will be imputed as described in Table 8, based on the eDiary question “Did you take any pain medication in the last 24 hours?”. If a subject replied to this question more than once on a given day, the following algorithm will be applied to retain only one answer per day:

- If there is at least one “Yes”, disregard all “No”;
- In a second step, only keep the last answer of the day.

**Table 8 Imputation of total daily dose of opioid analgesics based on answer to “Did you take any pain medication in the last 24 hours?” if no pain medications have been recorded in the eDiary**

Answer on Day X at time YY:YY	Conclusion	Imputed total daily dose of opioid analgesics
“Yes” + at least 1 medication recorded on Day X-1 after time YY:YY	No pain medication was taken on Day X	0 mg
“No”		
“Yes” + no medication recorded on Day X-1 after time YY:YY	Unknown if any pain medication was taken on Day X	Missing
Not available / missing		

The mean weekly dose at baseline is then derived as  $7 * (\text{sum of all total daily doses from study day } -28 \text{ to } -1) / \text{number of days with non-missing total daily dose}$ . Post-baseline, the mean weekly dose is derived in the same way, for each month, using the study days as defined in Table 4. In addition, the overall mean weekly dose from baseline to Month 6 is derived as the mean of the mean weekly dose at Month 1, Month 2, Month 3, Month 4,

Month 5 and Month 6. This overall score will only be derived for subjects who have a non-missing score available at each month.

By only using days with a non-missing total daily dose of opioid analgesics to derive the mean weekly dose, the implicit assumption is made that the total daily dose of opioid analgesics on days with missing data is the same as the average total daily dose of opioid analgesics on days with data recorded.

### 9.5.2 Use of significant rescue pain therapy from baseline up to Month 6

Significant rescue pain therapy is defined as any initiation or dose escalation of anticonvulsants (anti-epileptics), antidepressants (TCAs, SNRIs, SSRIs), or opioid analgesic drugs.

This endpoint is a binary variable (yes/no) where yes corresponds to at least 1 day on significant rescue pain therapy as reported in the eDiary by the subject between randomization and the Month 6 visit inclusive.

An initiation or dose escalation is defined as described in [Table 9](#). A day with at least one initiation or dose escalation is a day with use of significant rescue pain therapy.

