## 7 DEFINITIONS OF VARIABLES

### 7.1 Subject disposition

The subject disposition is detailed by the following definitions:

- Subjects screened (subjects with at least one screening date).
- Subjects re-screened (subjects with more than one screening date).
- Screen failures (subjects screened but not randomized).
- Subjects randomized (subjects with randomization number present in IRT system).
- Subjects treated (subjects with at least one dose of study treatment in eCRF study treatment log).
- Subjects who completed the study treatment (treated subjects without “Discontinuation” as reason for treatment stop in the eCRF study treatment log: record with DS.DSSCAT = END OF TREATMENT).
- Subjects who prematurely discontinued treatment (treated subjects with “Discontinuation” as reason for treatment stop in the eCRF study treatment log).
- Subjects who prematurely discontinued treatment due to the COVID-19 pandemic (treated subjects with “Discontinuation” as reason for treatment stop and “Is reason for discontinuation/interruption related to the COVID-19 pandemic?” ticked “Yes” in the eCRF study treatment log).
- Subjects who did not enter PTOP (subjects who prematurely discontinued study treatment, without any PTOP visit date).
- Subjects who entered PTOP (subjects who prematurely discontinued study treatment, with at least one PTOP visit date).
- Subjects who completed PTOP (subjects who entered PTOP, with a Month 6 PTOP visit date).
- Subjects who completed the study (subjects with “Did the subjects complete the study?” ticked “Yes” in the eCRF end of study status form: record with DS.DSSCAT = END OF STUDY).
- Subjects who completed the study without premature treatment discontinuation.
- Subjects who prematurely withdrew from the study (randomized subjects with “Did the subjects complete the study?” ticked “No” in the eCRF end of study status form).
- Subjects who prematurely withdrew from the study due to the COVID-19 pandemic (randomized subjects with “Did the subjects complete the study?” ticked “No” and “Is the reason the subject did not complete the study related to the COVID-19 pandemic?” ticked “Yes” in the eCRF end of study status form).
- Subjects who prematurely withdrew from the study prior to Month 6 (randomized subjects without Month 6 visit or Month 6 PTOP visit).

- Subjects who prematurely withdrew from the study due to the COVID-19 pandemic prior to Month 6.

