**Table 4 Daily scores used for derivation of monthly scores**

Monthly score	First study day	Last study day
Baseline	-28	-1
Month 1	3	30
Month 2	34	61
Month 3	64	91
Month 4	95	122
Month 5	125	152
Month 6	Month 6 visit* – 28 days	Month 6 visit* – 1 day

\* If Month 6 visit is on Day 198 or later (i.e., out of protocol defined visit window), use Day 169 to 196 instead. If Month 6 visit is on Day 168 or earlier (i.e., out of protocol defined visit window), the Month 6 score will be missing.

It may be noted that for subjects with a Month 6 visit performed earlier than Day 181, there will be an overlap between the 28 days used to derive the Month 5 monthly score and the 28 days used to derive the Month 6 monthly score.

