#### 15.4.1.2 Change from baseline to Month 6 in UACR

The ANCOVA after MI assuming MAR described in Section 15.3.3 will be used to analyze the change from baseline to Month 6 on the mFAS, on original values at baseline, Month 1, Month 3, Month 5, and Month 6.

Subjects with the baseline UACR value missing will be excluded from this analysis.

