## 15.4.2 Echocardiography-based endpoints

An ANCOVA model will be used to analyze the change from baseline to Month 6 of each echocardiography parameter on the mFAS. The following terms will be included in the model: baseline value, the two stratification factors (sex and ERT treatment status at screening), and the treatment group.

The estimate and the two-sided 95% CI will be calculated for the difference in the mean change from baseline to Month 6 between lucerastat and placebo.

This analysis will be implemented by the following SAS® code:

```
proc mixed;  
  class sex ertstatus treatment;  
  model chg = sex ertstatus bsl treatment;  
  lsmeans treatment / cl pdiff;  
run;
```

The analysis described above will be repeated on log-transformed values leading via the back-transformation  $x \rightarrow (e^x - 1) \times 100$  to treatment group results expressed as percent change from baseline and treatment effect estimate expressed as percent change relatively to placebo.

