## 15.4.3 Pain medication endpoints based on daily entries in eDiary

### 15.4.3.1 Subject mean weekly dose of opioid analgesics from baseline up to Month 6

The same approach (ANCOVA) as described in Section 15.4.2 will be used to analyze the overall mean weekly dose of opioid analgesics from baseline to Month 6 on the mFAS.

### 15.4.3.2 Use of significant rescue pain therapy from baseline up to Month 6

The same approach (CMH test) as described in Section 15.2.5.1 will be used to analyze this endpoint on the mFAS.

### 15.4.3.3 Total number of days on significant rescue pain therapy from baseline up to Month 6

Due to the expected distribution of this endpoint (count data) and the varying observation times per subject, this endpoint will be analyzed by determining the annualized rate of days on significant rescue pain therapy using a negative binomial regression model adjusted for the stratification factors.

The observation time (in years; defined in Section 9.5.3) will be used as an offset variable in the model in order to account for varying lengths of the observation period for each subject.

The treatment effect will be expressed as a rate ratio between lucerastat and placebo and will be presented with its 95% CI.

Since days with missing eDiary entries are excluded from the calculations (not imputed), the ARRT is unbiased in the presence of missing data as long as the unobserved rate of days with significant rescue pain therapy over the missing entries is the same as that observed over the non-missing entries. This assumption is considered reasonable given that measures have been put in place to minimize the risk of missing data [see protocol section 7.2.2.2.4].

This analysis will be implemented by the following SAS® code:

```
proc genmod;
  class sex ertstatus treatment;

  model nbdays = sex ertstatus treatment / dist=negbin link=log offset=ltime;
  * ltime = log(observation time);
  lsmeans treatment / cl exp;
  estimate "lucerastat - placebo" treatment 1 -1;
run;
```

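### The overall opioid dose is derived only for subjects with all six monthly scores, so the analysis labelled mFAS is a complete-case analysis

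*SAP*

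**What the plan says.** SAP 9.5.1 builds the endpoint in three steps. Daily opioid doses are converted to oral morphine equivalents. Each month's mean weekly dose is 7 times the sum of the daily doses divided by the number of days with a known dose, using the day ranges of Table 4. The overall score is the mean of the six monthly values, with the restriction "This overall score will only be derived for subjects who have a non-missing score available at each month".

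Table 4 ties the Month 6 range to the Month 6 visit and adds: "If Month 6 visit is on Day 168 or earlier (i.e., out of protocol defined visit window), the Month 6 score will be missing".

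SAP 15.4.3.1 says that the ANCOVA of Section 15.4.2 "will be used to analyze the overall mean weekly dose of opioid analgesics from baseline to Month 6 on the mFAS". Section 15.4.2 reads: "An ANCOVA model will be used to analyze the change from baseline to Month 6 of each echocardiography parameter on the mFAS". Its terms are baseline, sex, ERT status and treatment, and it has no imputation step.

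The one missing-data statement in 9.5.1 begins "By only using days with a non-missing total daily dose of opioid analgesics to derive the mean weekly dose". It assumes that unrecorded days resemble recorded ones. It says nothing about months with no usable day at all.

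**The concern.** Whether a subject has all six monthly scores is settled after randomization. A rule that conditions on it compares a selected part of each arm, although the analysis is labelled mFAS. It also discards up to five months of recorded doses per excluded subject from this score.

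The SAP gives reasons to think that loss may be related to pain. Section 9.5.2 uses neuropathic pain as a recorded reason for a missed diary, and Section 8.2 lists lack of efficacy among the reasons for stopping treatment. For the primary endpoint, taken from the same diary, the SAP imputes under a not-at-random assumption in the lucerastat arm. For the opioid dose it deletes the subject. If the subjects lost differ in opioid use, and are lost unequally between arms, the treatment contrast shifts.

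**Working it through.** **No design figure to reproduce.** The documents state no effect, SD, missingness rate or power for this endpoint. The primary endpoint's power (87.2%; 66 vs 33, difference 2, SD 3, two-sided 5%) reproduces at 87.20% with a noncentral t calculation, but does not bear on this point.

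**Who is excluded.**
- A subject who leaves the study or stops the eDiary early enough to have no Month 6 score: excluded.
- A subject who finishes but has one month with no usable day: excluded.
- A subject whose Month 6 visit is on Day 168 or earlier: excluded through Table 4. For plasma Gb3, Table 5 counts Day 168 as Month 6.
- A subject with a single usable day in each month: kept, because 9.5.1 sets no minimum number of days. By contrast, the pain score needs 4 of 7 days in at least 3 of 4 weeks, and the diarrhea count needs 21 days.
- A subject who stops treatment but continues the eDiary: kept. Protocol 5.1.9 does not treat such subjects as withdrawn. Protocol 7.2.2.2.4 asks them to go on with the eDiary to the scheduled Month 6 visit, and protocol Table 6 has pain medication recorded daily in the PTOP. This takes the Month 6 PTOP visit as the Table 4 anchor.

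**How comparable endpoints are treated.** The rescue-day rate (SAP 9.5.3, 15.4.3.3) uses each subject's recorded diary days, with observation time as an offset. For UACR, SAP 15.4.1.2 says: "The ANCOVA after MI assuming MAR described in Section 15.3.3 will be used". Both keep subjects with partial follow-up.

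**Illustrative loss.** Let w be the proportion leaving before Month 6 and g the chance of a wholly empty month, independent across months, among those who stay. Both are assumptions. The share kept is (1 − w)(1 − g)^6. N = 118 randomized (SAP Section 2) stands in for the mFAS.

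| w | g | share kept | of 118 |
|---|---|---|---|
| 5% | 0 | 0.950 | 112 |
| 10% | 0 | 0.900 | 106 |
| 20% | 0 | 0.800 | 94 |
| 0 | 1% | 0.941 | 111 |
| 0 | 5% | 0.735 | 87 |
| 10% | 2% | 0.797 | 94 |

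Independence makes the g rows pessimistic. If the same 5% of subjects account for all the empty months, the loss is 5% (about 112 kept), not 26%.

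**Illustrative bias.** Suppose that those lost would have averaged k SD above those kept, with loss wL on lucerastat and wP on placebo. Each arm's full mean exceeds its completer mean by k times its loss rate. For lucerastat minus placebo, the completer contrast minus the full contrast is therefore k(wP − wL).
- wL = 5%, wP = 15%, k = 1: 1 × (0.15 − 0.05) = 0.10 SD.
- wL = 15%, wP = 5%, k = 1: −0.10 SD.
- Equal loss and equal k in both arms: 0.

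If k differs by arm, the shift is kP·wP − kL·wL, which can be non-zero even with equal loss. The sign cannot be known in advance.

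**The case against.** The strongest reply is that little is lost and much is covered elsewhere. Diary alarms and non-compliance alerts are in place, and a month is lost only if no day in its range is usable. Early leavers still contribute to any rescue use, to the rescue-day rate and, if they stopped treatment or started ERT, to time to treatment failure. ANCOVA on the mFAS without imputation is also planned for echocardiography, BPI-SF items 5 and 9, CESD-R-20 and SF-36. All of this stands, and it keeps the point small. It does not justify the rule. For those other endpoints, a subject without a Month 6 value has no Month 6 outcome to use. Here up to five observed monthly outcomes are set aside.

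Three stronger readings are tempting, and the documents do not support them.
- A reader might infer that everyone who stops early is removed. Treatment discontinuers who keep the diary are retained.
- A reader might infer a contradiction with the general commitment to use all available data. SAP Section 14 allows exceptions where specified, and 9.5.1 specifies one. The treatment-policy estimands cover only the primary and secondary endpoints.
- A reader might take 3–5% missing per month to mean 17–26% excluded (1 − 0.97^6 and 1 − 0.95^6). Neither the rate nor the independence is in the documents.

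That those lost have poor pain control is likewise an inference.

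**Conclusion.** The point holds as a matter of derivation: the overall opioid dose is analysed in complete cases only, with no stated reason, imputation or sensitivity analysis. The number excluded is unknown. About 12 of 118 would go at an assumed 10% withdrawal with no other gaps (118 − 106). The shift would be about 0.1 SD if loss differs by 10 percentage points between arms and those lost differ by 1 SD, and zero if loss and dose gap are equal across arms. The endpoint is outside the fixed testing sequence, so the primary result and type I error control are untouched. This is a cheap improvement, not a threat to the trial's main conclusion.

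**What to change.** Drop the all-six-months condition for the main analysis. Use the monthly mean weekly doses that 9.5.1 already derives, for all mFAS subjects with a baseline and at least one post-baseline monthly score, in one of two ways:
- the MMRM of SAP 15.2.5.5, with the treatment effect averaged over Months 1 to 6; or
- the MAR multiple imputation of SAP 15.3.3 before the ANCOVA, with all six months in the imputation model and a lower bound of zero.

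Keep the six-month completer score as a sensitivity analysis, and report the number excluded from it by arm.

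Pooling all recorded days into one average looks simpler but is weaker. The ANCOVA has no offset, so a subject with 28 days would count as much as one with 180, and the dose would be assumed constant after the diary stops.

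The cost is a revised derivation and one more model run. The main downside is reliance on missing at random, which may fail if pain drives loss. The completer analysis and the counts by arm let a reader judge how much depends on it.

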**Table 9 Significant rescue pain therapy: definition of initiation and dose escalation**

Initiation	Opioid analgesics	Only defined for subjects who have not taken any opioid analgesics between study day -28 and -1 as any day from study day 1 onwards with a total daily dose of opioid analgesics > 0 mg.
	Anticonvulsant / Antidepressant	For each anticonvulsant / antidepressant, any day from study day 1 onwards with an anticonvulsant / antidepressant medication recorded which has not been taken between study day -28 and -1.
Dose escalation	Opioid analgesics	Any day from study day 1 onwards with a total daily dose of opioid analgesics > maximum total daily dose of opioid analgesics between study day -28 and -1.
	Anticonvulsant / Antidepressant	For each anticonvulsant / antidepressant, any day from study day 1 onwards with an anticonvulsant / antidepressant medication with a daily dose > maximum daily dose between study day -28 and -1.

Days with missing diary entries (derived using [Table 8](#)), are only considered as days with significant rescue pain medication if the closest available non-missing day before the day in question is a day with significant rescue pain medication (derived using [Table 9](#)) and the subject answered “Too much neuropathic pain” to the question “You missed at least one diary. Why?” on the closest available non-missing day after the day in question.

### **9.5.3 Total number of days on significant rescue pain therapy from baseline up to Month 6**

The annualized rate of days with significant rescue therapy (ARRT) is defined as the number of days on significant rescue pain therapy as reported in the eDiary per subject-year from randomization up to the Month 6 visit inclusive.

For the statistical analysis of the ARRT, the following two variables will be used:

- The subject's number of days on significant rescue pain therapy as reported in the eDiary up to the Month 6 visit inclusive;
- The observation time expressed in years as the total number of days with non-missing eDiary entries up the Month 6 visit inclusive, divided by 365.25.

Days with significant rescue pain therapy are derived as described in Section 9.5.2.

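### The annualized rate of rescue-therapy days counts some missing-diary days in the numerator but leaves them out of the observation time, so rates are inflated and can exceed 365 days per year

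*SAP*

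**What the plan says.** SAP 9.5.3 builds the rate from two variables. The first is "The subject's number of days on significant rescue pain therapy as reported in the eDiary up to the Month 6 visit inclusive". The second is "The observation time expressed in years as the total number of days with non-missing eDiary entries up the Month 6 visit inclusive", divided by 365.25. The section then says how the numerator days are found: "Days with significant rescue pain therapy are derived as described in Section 9.5.2".

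Section 9.5.2 contains a rule for missing diary days, placed directly under Table 9. Such days "are only considered as days with significant rescue pain medication if the closest available non-missing day before the day in question" was itself a rescue day, and if the subject named excessive neuropathic pain as the reason for the missed diary "on the closest available non-missing day after the day in question". Missing status is taken from Table 8, whose relevant category reads "Unknown if any pain medication was taken on Day X".

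Section 15.4.3.3 fits a negative binomial model in which the observation time "will be used as an offset variable in the model in order to account for varying lengths of the observation period for each subject". It defends the handling of missing data as follows: "Since days with missing eDiary entries are excluded from the calculations (not imputed), the ARRT is unbiased in the presence of missing data", provided the rate of rescue days over the missing entries equals the rate over the recorded ones.

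**The concern.** A rate is interpretable only if the events and the time at risk cover the same days. Here a missing day that meets the 9.5.2 conditions adds one event and no time. The subjects affected are those who skip the diary because of pain while on rescue therapy, so the inflation is tied to the outcome being measured. If such days are more frequent in one arm, the rate ratio between lucerastat and placebo moves for a reason unrelated to the true rates. Should lucerastat relieve pain, placebo would be expected to have more of these days, and the mismatch would then flatter lucerastat.

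There is also a reproducibility problem. A programmer who follows 9.5.2 and 9.5.3 gets one estimate, and a programmer who follows the text of 15.4.3.3 gets another.

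**Working it through.** The SAP gives no figure for this endpoint, so there is nothing to reproduce. The check follows the definitions and then puts numbers to them.

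**Inputs.** For one subject, let N be the diary days with non-missing entries (9.5.3), R the rescue days among them (9.5.2, Table 9), and m the missing days classed as rescue under the 9.5.2 rule. The year length of 365.25 days comes from 9.5.3. The documents give no values for R or m, so those below are assumptions. Where a full period is needed, N + m = 183 days, the nominal Month 6 study day in SAP Table 5.

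**Formulas.**
- As written: 365.25 × (R + m) / N
- Counted in both terms: 365.25 × (R + m) / (N + m)
- Left out of both terms: 365.25 × R / N

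The inflation factor is (N + m)/N against the second version and (R + m)/R against the third. The rate as written exceeds 365.25 exactly when m > N − R, that is, when the added missing days outnumber the recorded non-rescue days. Neither consistent version can exceed 365.25.

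**Per-subject examples (days per year).**

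| N | R | m | As written | In both | In neither |
|---|---|---|---|---|---|
| 150 | 60 | 20 | 80/150 × 365.25 = 194.8 | 80/170 × 365.25 = 171.9 | 60/150 × 365.25 = 146.1 |
| 100 | 80 | 30 | 110/100 × 365.25 = 401.8 | 110/130 × 365.25 = 309.1 | 80/100 × 365.25 = 292.2 |
| 163 | 60 | 20 | 179.3 | 159.7 | 134.4 |
| 163 | 153 | 20 | 387.7 | 345.3 | 342.8 |

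In the first row the inflation is 194.8/171.9 = 1.13 against counting in both and 194.8/146.1 = 1.33 against counting in neither.

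**Range over m in a 183-day period.** Against counting in both, the inflation is 183/178 = 2.8% for m = 5, 183/173 = 5.8% for m = 10, 183/163 = 12.3% for m = 20, and 183/153 = 19.6% for m = 30.

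**Effect on the rate ratio.** Take one representative subject per arm, with R = 40 on lucerastat and R = 60 on placebo, over 183 days.
- m = 10 in both arms: as written (50/173)/(70/173) = 0.714; in both 50/70 = 0.714; in neither 40/60 = 0.667.
- m = 5 on lucerastat and 20 on placebo: as written (45/178)/(80/163) = 0.515; in both 45/80 = 0.563; in neither (40/178)/(60/163) = 0.610.

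With equal m the mismatch cancels against the counted-in-both version. With unequal m it does not: 0.515 is the counted-in-both ratio multiplied by 163/178.

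**Can the missing-day rule be meant only for the yes/no endpoint of 9.5.2?** No. The rule requires an earlier recorded rescue day, and Table 9 allows rescue days only from study day 1 onwards. That earlier day already makes the subject a yes, so the rule can never change the binary result. It can matter only where days are counted or treated one by one, and the count in 9.5.3 is such a use.

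**The case against.** The strongest reply is that this is a conflict between sections and not a settled biased estimator. Section 15.4.3.3 is the analysis section and says missing days are not imputed, and 9.5.3 refers to days as reported in the eDiary. If 15.4.3.3 governs, the mismatch disappears. This does not succeed. Section 9.5.3 refers to 9.5.2 without exception, 9.5.2 uses the same reporting phrase beside its missing-day rule, and the rule would have no effect on the yes/no endpoint. What remains is that the two statements cannot both be followed.

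Several narrower points stand:
- The documents do not say how many days meet both conditions. The protocol's reminders, nightly transfers and non-compliance alerts (7.2.2.2.4) are intended to keep missing days few, and with 5 to 10 qualifying days the inflation against counting in both is 3% to 6%.
- A rate above 365 arises only for subjects on rescue on nearly every recorded day.
- Against the counted-in-both version, the ratio is distorted only when such days differ between arms.
- Table 8 also treats a day as missing when the subject answered yes but no medication was recorded in the preceding interval. Section 9.5.3 does not say whether such a day has a non-missing entry, so for that type of day the mismatch depends on a definition the SAP does not give.
- Leaving the days out of both terms is not the only consistent choice. The 9.5.2 rule regards them as probable rescue days, so dropping them may understate the rate for subjects in severe pain.

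**Conclusion.** The concern holds. As defined in 9.5.2 and 9.5.3, the count and the observation time cover different days, and the unbiasedness statement in 15.4.3.3 does not describe that estimator. For an affected subject the rate is always inflated, by (N + m)/N or (R + m)/R depending on the comparator. In the milder example that is 13% or 33%; in the extreme one the rate is 402 days per year. The true size is unknown because it rests on assumed values of R and m, and the direction and size of any effect on the rate ratio depend on how the qualifying days fall between arms.

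This is an exploratory efficacy endpoint outside the fixed testing sequence, so the primary and secondary tests are untouched by the mismatch. It should be corrected because the definition permits impossible values and the sections contradict each other.

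**What to change.** Use one set of days in both terms.

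- **Main analysis.** State in 9.5.3 that, for this rate, missing-diary days contribute to neither the count nor the observation time. This is what 15.4.3.3 already claims, and its text can then stand. Define non-missing in 9.5.3 by reference to Table 8, so that both terms use the same classification.
- **Sensitivity analysis.** Add the missing days classed as rescue under 9.5.2 to both the count and the observation time, and refit the same model. This addresses the worry that pain-related missing days are not like the recorded ones.
- **Reporting.** Tabulate the number of missing days classed as rescue by arm, so that a reader can see whether the choice matters.

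The main change costs a sentence or two in 9.5.3 and one line of code. The sensitivity analysis is a second run of the existing model with a different count and offset. No new data are needed. The change should be made before the randomization code is broken.
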